8.7.7 Other Analyses

Descriptive summary analyses will be provided for medical history and risk factor variables at baseline.

The extent of study drug treatment exposure and compliance will be descriptively summarized by treatment for the safety set.

8.8 Handling of Missing Data

Details on how missing dates for AEs or concomitant medications will be handled will be specified in the SAP.

For the primary analysis, an MI strategy (as specified in [Section 8.7.3.1](#)) will be used for handling missing data. An MMRM assuming missing at random (MAR) will be used as a sensitivity analyses. A reference-based MI strategy assuming missing not at random (MNAR) will be performed as a sensitivity analysis for superiority. The details of missing data handling will be specified in the SAP.

8.9 Interim Analyses

No interim analyses are planned for this trial.

8.10 Data Quality Assurance

- All patient data relating to the trial will be recorded on printed case report forms (CRFs) or eCRFs unless transmitted to the sponsor or designee electronically (eg, laboratory data). The investigator is responsible for verifying that data entries are accurate and correct by physically or electronically signing the CRF.
- Guidance on completion of CRFs will be provided in a set of CRF Completion Guidelines.
- The investigator must permit trial-related monitoring, audits, IRB/IEC review, and regulatory agency inspections and provide direct access to source data documents.
- Monitoring details describing strategy (eg, risk-based initiatives in operations and quality, such as Risk Management and Mitigation Strategies and Analytical Risk-Based Monitoring), methods, responsibilities and requirements, including handling of noncompliance issues and monitoring techniques (central, remote, or on-site monitoring) are provided in separate trial documents.
- The sponsor or designee is responsible for the data management of this trial, including quality checking of the data.
- The sponsor assumes accountability for actions delegated to other individuals (eg, contract research organizations).
- Records and documents, including signed ICFs, pertaining to the conduct of this trial must be retained by the investigator for 25 years after the signature of the final trial report unless local regulations or institutional policies require a longer retention period. No records may be destroyed during the retention period without the written approval of the sponsor. No records may be transferred to another location or party without written notification to the sponsor.

8.10.1 Data Management

As part of the responsibilities assumed by participating in the trial, the investigator agrees to maintain adequate case histories for the patients treated as part of the research under this protocol. The investigator agrees to maintain accurate eCRFs and source documentation as

part of the case histories. These source documents may include medical charts, the patient's eDiary, and laboratory reports ([Section 13.8](#)).

PPD will supply the eCRF, whose access will be limited to personnel directly participating in the trial, and all eCRFs should be completed in English.

All eCRF information is to be filled in. If an item is not available or is not applicable, this fact should be indicated per the guidelines for completion. Blank spaces should not be present unless otherwise directed.

Clinical data management will be performed in accordance with applicable PPD standards and data cleaning procedures to ensure the integrity of the data (eg, removing errors and inconsistencies in the data). Adverse events and concomitant medication terms will be coded using MedDRA and WHO Drug, respectively. After database lock, each site will receive their site-specific eCRF data as entered into Medidata Rave for the trial, including full discrepancy and audit history. Additionally, a copy of all data from the trial will be created and sent to the sponsor for storage. In all cases, patient initials and their date of birth will not be collected.

9 Ethics

9.1 Independent Ethics Committee or Institutional Review Board

Federal regulations and the International Council for Harmonisation (ICH) guidelines require that approval be obtained from an IRB/IEC before participation of human patients in research studies. Before trial onset, any information related to this trial or provided to the patient (eg, the protocol, informed consent, advertisements for recruitment of trial participants, any other written information) must be approved by the IRB/IEC. Documentation of all IRB/IEC approvals and of the IRB/IEC compliance with ICH harmonised tripartite guideline E6(R1): Good Clinical Practice (GCP) will be maintained by the site and will be available for review by the sponsor or its designee.

All IRB/IEC approvals should be signed by the IRB/IEC chairman or designee and must identify the IRB/IEC name and address, the clinical protocol by title or protocol number or both, and the date approval or a favorable opinion was granted.

The investigator is responsible for providing written summaries of the progress and status of the trial at intervals not exceeding 1 year or otherwise specified by the IRB/IEC.

The investigator must promptly supply the sponsor or its designee, the IRB/IEC, and, where applicable, the institution, with written reports on any changes significantly affecting the conduct of the trial or increasing the risk to patients.

9.2 Ethical Conduct of the Trial

The trial will be performed in accordance with the ethical principles that have their origin in the Declaration of Helsinki, ICH GCP, and all applicable regulations.

9.3 Patient Information and Consent

A written informed consent in compliance with regulatory authority regulations and/or US Title 21 Code of Federal Regulations (CFR) Part 50 shall be obtained from each patient before entering the trial or performing any unusual or nonroutine procedure. An informed consent template will be provided by the sponsor to investigative sites. If any institution-specific modifications to trial-related procedures are proposed or made by the site, the consent should be reviewed by the sponsor or its designee or both before submitting the

revised ICF to the IRB/IEC. If the ICF is revised during the course of the trial, all active patients must sign the revised form.

Before recruitment and enrollment, each potential patient will be given a full explanation of the trial and be allowed to read the approved ICF. Once the investigator is assured that the patient understands the implications of participating in the trial, the patient will be asked to give consent to participate in the trial by signing the ICF.

The investigator shall retain the signed original ICF(s) and give a copy of the signed original form to the patient.

CCI

10 Investigator's Obligations

The following administrative items are meant to guide the investigator in the conduct of the trial but may be subject to change based on industry and government standard operating procedures, working practice documents, or guidelines. Changes will be reported to the IRB/IEC but will not result in protocol amendments.

10.1 Confidentiality

All laboratory specimens, evaluation forms, reports, and other records will be identified in a manner designed to maintain patient confidentiality. All records will be kept in a secure storage area with limited access. Clinical information will not be released without the written permission of the patient, except as necessary for monitoring and auditing by the sponsor, its designee, regulatory authorities (eg, the US FDA), or the IRB/IEC.

The investigator and all employees and coworkers involved with this trial may not disclose or use for any purpose other than performance of the trial, any data, record, or other unpublished, confidential information disclosed to those individuals for the purpose of the trial. Written agreement from the sponsor or its designee must be obtained before the disclosure of any said confidential information to other parties.

10.2 Data Protection

All personal data collected and/or processed in relation to this trial will be handled in compliance with all applicable Privacy & Data Protection laws and regulations, including the General Data Protection Regulation (GDPR). The trial sponsor is the Sanofi company responsible for ensuring compliance with this matter, when processing data from any individual who may be included in the Sanofi databases, including investigators, nurses, experts, service providers, Ethics Committee members, etc.

When archiving or processing personal data pertaining to the investigator and/or to the patients, the sponsor will take all appropriate measures to safeguard and prevent access to this data by any unauthorized third party.

Protection of Patient Data

The data collected must be adequate, relevant, and not excessive, in relation to the purposes for which they are collected. Each category of data must be properly justified and in line with the trial objective.

This trial will attempt to represent a diverse set of patients with T2DM and renal impairment, as they represent a growing proportion of the patient population, are historically under-represented in clinical trials, and are disproportionately affected by T2DM and renal impairment. For example, ethnic minority groups are known to have a higher prevalence of T2DM and end-stage renal failure compared with the white majority population ([Mathur et al 2018](#)).

Protection of Data Related to Professionals Involved in the Trial

- Personal data (eg, contact details, affiliation details, job title and related professional information, role in the trial, professional resume, training records) are necessary to allow Sanofi to manage involvement in the trial and/or the related contractual or pre-contractual relationship. They may be communicated to any company of the Sanofi group (“Sanofi”) or to Sanofi service providers, where needed.
- Personal data can be processed for other trials and projects. At any time, objection to processing can be made by contacting the Sanofi Data Protection Officer (link available at Sanofi.com).
- In case of refusal to the processing of personal data by or on behalf of Sanofi, it will be impossible to involve the professionals in any Sanofi trial. In case the professionals have already been involved in a Sanofi trial, they will not be able to object to the processing of their personal data as long as they are required to be processed by applicable regulations. The same rule applies in case the professionals are listed on a regulatory agencies' disqualification list.
- Personal data can be communicated to the following recipients:
 - Personnel within Sanofi or partners or service providers involved in the trial.
 - Judicial, administrative, and regulatory authorities, in order to comply with legal or regulatory requirements and/or to respond to specific requests or orders in the framework of judicial or administrative procedures. Contact details and identity may also be published on public websites in the interest of scientific research transparency.

- Personal data may be transferred towards entities located outside the Economic European Area, in countries where the legislation does not necessarily offer the same level of data protection or in countries not recognized by the European Commission as offering an adequate level of protection. Those transfers are safeguarded by Sanofi in accordance with the requirement of European law, including the following:
 - The standard contractual clauses of the European Commission for transfers towards our partners and service providers.
 - Sanofi's Binding Corporate Rules for intra-group transfers.
- Professionals are able to lodge a complaint with Sanofi leading Supervisory Authority, the "Commission Nationale de l'Informatique et des Libertés" (CNIL) or with any competent local regulatory authority.
- Personal data of professionals will be retained by Sanofi for up to 30 years unless further retention is required by applicable regulations.
- In order to facilitate the maintenance of investigators' personal data, especially if they contribute to studies sponsored by several pharmaceuticals companies, Sanofi participates in the Shared Investigator Platform (SIP) and in the TransCelerate Investigator Registry (IR) project (<https://transceleratebiopharmainc.com/initiatives/investigator-registry/>). Therefore, personal data will be securely shared by Sanofi with other pharmaceutical company members of the TransCelerate project. This sharing allows investigators to keep their data up-to-date once, for access by all pharmaceutical companies participating in the project, with the right to object to the transfer of the data to the TransCelerate project.
- Professionals have the right to request access to and rectification of their personal data, as well as their erasure (where applicable) by contacting the Sanofi Data Protection Officer: Sanofi DPO - [name] (to contact Sanofi by email, visit <https://www.sanofi.com/en/our-responsibility/sanofi-global-privacy-policy/contact>).

10.3 Financial Disclosure and Obligations

Investigators and sub-investigators are required to provide financial disclosure information to allow the sponsor to submit the complete and accurate certification or disclosure statements per requirements of local or national regulatory authorities and/or under 21 CFR 54.

In addition, the investigator must provide to the sponsor a commitment to promptly update this information if any relevant changes occur during the course of the investigation and for 1 year following the completion of the trial.

Neither the sponsor nor PPD is financially responsible for further testing or treatment of any medical condition that may be detected during the screening process. In addition, in the absence of specific arrangements, neither the sponsor nor PPD is financially responsible for further treatment of the patient's disease.

10.4 Investigator Documentation

Before beginning the trial, the investigator will be asked to comply with ICH E6(R2) Section 8.2 and Title 21 of the CFR and/or with local or national regulatory requirements by providing all essential documents, including but not limited to the following:

- IRB/IEC approval.
- Original investigator-signed agreement page of the protocol.
- Curriculum vitae for the investigator and each sub-investigator.
- Financial disclosure information to allow the sponsor or designee to submit complete and accurate certification. In addition, investigators must provide to the sponsor or designee a commitment to promptly update this information if any relevant changes occur during the course of the investigation and for 1 year after the completion of the trial.
- IRB-/IEC-approved informed consent, samples of site advertisements for recruitment for this trial, and any other written information regarding this trial that is to be provided to the patient.
- Signed Clinical Trial Agreement.

10.5 Trial Conduct

The investigator agrees that the trial will be conducted according to the principles of ICH E6(R2). The investigator will conduct all aspects of this trial in accordance with all national, state, and local laws or regulations. Trial information from this protocol will be posted on publicly available clinical trial registers before enrollment of patients begins.

10.6 Adverse Events and Trial Report Requirements

The investigator agrees to submit reports of SAEs to the sponsor or designee and/or IRB/IEC according to the timeline and method outlined in the protocol ([Section 13.5.4](#)). In addition, the investigator agrees to submit annual reports to the site IRB/IEC as appropriate.

10.7 Investigator's Final Report

Upon completion of the trial, the investigator, where applicable, should inform the institution; the investigator/institution should provide the IRB/IEC with a summary of the trial's outcome and the sponsor and regulatory authority(ies) with any reports required.

11 Trial Management

11.1 Monitoring

11.1.1 External Data Monitoring Committee

No data monitoring committee is planned for this trial.

11.1.2 Monitoring of the Trial

The clinical monitor, as a representative of the sponsor, has the obligation to follow the trial closely. In doing so, the monitor will visit the investigator and site at periodic intervals, in addition to maintaining necessary phone and letter contact. The monitor will maintain current personal knowledge of the trial through observation, review of trial records and source documentation, and discussion of the conduct of the trial with the investigator and personnel.

In the event a clinical monitor cannot visit the site in a timely manner due to the coronavirus disease 2019 (COVID-19) pandemic, alternative monitoring approaches, such as remote source data verification may be used to ensure data quality and integrity and maintain patient safety. Alternative monitoring approaches should be used only where allowed by the local health authority, privacy laws, and permitted by the IRB/IEC.

The medical monitor and sponsor will hold meetings at regular intervals to review AEs, unless an SAE is noted and reported as described in [Section 6.2.6.5](#).

All aspects of the trial will be carefully monitored, by the sponsor or its designee, for compliance with applicable government regulation with respect to current GCP and current standard operating procedures.

11.1.3 Inspection of Records

Investigators and institutions involved in the trial will permit trial-related monitoring, audits, IRB/IEC review, and regulatory inspections by providing direct access to all trial records. In the event of an audit, the investigator agrees to allow the sponsor, representatives of the sponsor, or a regulatory agency (eg, US FDA) access to all trial records.

The investigator should promptly notify the sponsor and PPD of any audits scheduled by any regulatory authorities and promptly forward copies of any audit reports received to the sponsor.

11.2 Management of Protocol Amendments and Deviations

11.2.1 Modification of the Protocol

Any changes in this research activity, except those necessary to remove an apparent, immediate hazard to the patients, must be reviewed and approved by the sponsor or its designee. Amendments to the protocol must be submitted in writing to the investigator's IRB/IEC for approval before patients can be enrolled into an amended protocol.

11.2.2 Protocol Deviations

The investigator or designee must document and explain in the patient's source documentation any deviation from the approved protocol. The investigator may implement a deviation from, or a change of, the protocol to eliminate an immediate hazard to trial patients without prior IRB/IEC approval. As soon as possible after such an occurrence, the implemented deviation or change, the reasons for it, and any proposed protocol amendments should be submitted to the IRB/IEC for review and approval, to the sponsor for agreement, and to the regulatory authorities, if required.

A deviation from the protocol is an unintended or unanticipated departure from the procedures or processes approved by the sponsor and the IRB/IEC and agreed to by the investigator. A significant deviation occurs when there is nonadherence to the protocol by the patient or investigator that results in a significant, additional risk to the patient. Significant deviations can include nonadherence to inclusion or exclusion criteria or nonadherence to local regulations or ICH GCP guidelines, and will lead to the patient being withdrawn from the trial ([Section 4.4](#)).

Protocol deviations will be documented by the clinical monitor throughout the course of monitoring visits. Principal investigators will be notified in writing by the monitor of deviations. The IRB/IEC should be notified of protocol deviations as applicable.

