4.4.1.1 Permanent Discontinuation

In rare instances, it may be necessary for a patient to permanently discontinue the study drug.

Patients will be followed up according to the trial procedures specified in this protocol up to the scheduled date of trial completion, or up to recovery or stabilization of any AE, whichever comes last.

If possible, and after the permanent discontinuation of study drug treatment, patients will be assessed using the procedure normally planned for the last dosing day with the study drug. See the SoE ([Section 13.2](#)) for data to be collected at the time of study drug discontinuation and follow-up and for any further evaluations that need to be completed.

All cases of permanent study drug discontinuation must be recorded by the investigator in the appropriate pages of the eCRF when confirmed.

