4.4.3 Handling of Withdrawals

Patients are free to withdraw from the trial at any time upon request. Their participation in the trial may be stopped at any time at the discretion of the investigator or at the request of the sponsor.

If the patient withdraws consent for disclosure of future information, the sponsor may retain and continue to use any data collected before such a withdrawal of consent.

If a patient withdraws from the trial, they may request destruction of any samples taken and not tested, and the investigator must document this in the site trial records.

Patients who permanently discontinue the study drug or active participation in the trial will no longer receive the study drug. When a patient withdraws from the trial, the reason(s) for withdrawal shall be recorded by the investigator on the relevant page of the eCRF.

A patient may withdraw from the trial or study drug treatment for circumstances that include, but are not limited to, the following:

- The patient intends to become pregnant.
- The patient may be withdrawn at the discretion of the investigator due to noncompliance or due to a safety concern.

- The patient will be withdrawn if they are starting any drugs that interfere with glucose metabolism (eg, systemic glucocorticoid therapy).
- If the fasting or the mean SMPG value is >300 mg/dL, the investigator will schedule an unplanned visit as soon as possible, to obtain confirmatory FPG and investigate the cause. If no apparent or intercurrent cause is detected, the patient may be withdrawn.
- The patient has recurrent severe hypoglycemia or recurrent nocturnal hypoglycemia during the treatment period that poses a potential risk to the patient, as judged by the investigator.
- The patient needs dialysis, as judged by the investigator.
- The patient is unable to comply with the trial protocol, at the investigator's discretion.

All patients who discontinue study drug treatment will be followed up per the methods specified in this protocol. All patients who withdraw from the trial prematurely will, as soon as possible, undergo all end-of-trial and follow-up assessments/procedures at a visit that should be identified as "the early trial discontinuation visit." Patients who fail to return for final assessments will be contacted by the site in an attempt to have them comply with the protocol requirements.

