6.1 Efficacy Assessments

6.1.1 HbA1c Measurements

The primary efficacy endpoint and some secondary and exploratory endpoints will be assessed by HbA1c measurement. Blood samples will be collected to measure HbA1c at the different time points specified in the SoE ([Section 13.2](#)) at the central laboratory.

For the eligibility assessment, HbA1c levels will be measured during the screening period (Week –2, Visit 1). For the efficacy assessments of the trial, HbA1c levels will be measured at baseline/randomization, at the end of the titration period (Week 12; Visit 14), and at the end of the treatment period (Week 24, Visit 17; [Section 13.2](#)). If a patient needs to receive rescue antidiabetic therapy, the HbA1c assessment should be performed before they are introduced. In addition, in case of study drug treatment discontinuation, patients will be followed up per protocol. In case of trial discontinuation, HbA1c assessment will be performed at the time of withdrawal, if possible.

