8.1.2 Estimands

Attributes for the primary and supplementary estimands with the strategies used for handling ICEs are presented in [Table 8-2](#).

Table 8-2 Primary and Supplementary Estimands

Estimand 1a (Primary)	
Estimand Description	Difference in the mean change from baseline to Week 24 in HbA1c level (Gla-300 vs IDeg-100) in insulin-naïve patients with T2DM and renal impairment who have glycemic levels above target with OADs with or without GLP-1 RA (oral or injectable), regardless of discontinuation of study drug treatment due to any reasons and use of rescue therapies
Target Population	Insulin-naïve patients with T2DM and renal impairment who have glycemic levels above target with OADs with or without GLP-1 RA (oral or injectable) as defined by the inclusion/exclusion criteria (Section 4)
Treatment Conditions	Once daily, SC self-injection of Gla-300 versus IDeg-100 with the planned dose modifications outlined in Section 5.5.1 
• Gla-300: Insulin glargine 300 U/mL• IDeg-100: Insulin degludec 100 U/mL
Endpoint	Change in HbA1c level from baseline to Week 24
Population Level Summary	Difference in the mean change in HbA1c level from baseline to Week 24 between Gla-300 and IDeg-100

Estimand 1a (Primary)	
ICEs and Strategies	Treatment policy strategy for handling the ICEs in Table 8-1
Rationale	Using the treatment policy strategy for handling ICEs is considered appropriate for showing superiority (ICH E9 R1), which allows switching the objective of a trial from non-inferiority to superiority (CPMP guideline)
Estimand 1b (Supplementary)	
Estimand Description	Difference in the mean change from baseline to Week 24 in HbA1c level (Gla-300 vs IDeg-100) in insulin-naïve patients with T2DM and renal impairment who have glycemic levels above target with OADs with or without GLP-1 RA (oral or injectable), assuming no discontinuation of study drug treatment due to any reasons and use of rescue therapies
Target Population	Insulin-naïve patients with T2DM and renal impairment who have glycemic levels above target with OADs with or without GLP-1 RA (oral or injectable) as defined by the inclusion/exclusion criteria (Section 4)
Treatment Conditions	Once daily, SC self-injection of Gla-300 versus IDeg-100 with the planned dose modifications outlined in Section 5.5.1 
 • Gla-300 arm: Insulin glargine 300 U/mL • IDeg-100 arm: Insulin degludec 100 U/mL

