8.7.3 Analysis of Primary Endpoints

8.7.3.1 Main Estimation of Primary Estimand

For the primary efficacy endpoint (ie, change from baseline to Week 24 in HbA1c level), data collected after the ICEs will be included in the analysis based on the ITT set. Missing data will be handled using a multiple imputation (MI) strategy depending on treatment-completion status:

- Missing data from patients discontinuing the study drug treatment will be imputed using data from patients also discontinuing the study drug treatment but who have their endpoint assessed within each treatment arm.
- Missing data from patients completing the 24-week treatment period will be imputed using a model estimated from data observed in other patients completing the study drug treatment within each treatment arm.

The following two-step approach will be used for the MI:

- Step 1: The Markov chain Monte Carlo (MCMC) method will be used to impute intermediate missing data to create a monotone missing data pattern.
- Step 2: Using the imputed datasets with monotone missing data pattern obtained from Step 1, missing data will then be imputed using the sequential regression method.

The imputation model for Step 1 will include the treatment arm, baseline HbA1c value, and HbA1c values at Week 12 and Week 24. The imputation model for Step 2 will include the same variables as in Step 1 with the randomization strata (other than the categorized HbA1c).

For each multiply imputed dataset, an analysis of covariance (ANCOVA) model will be performed; this analysis will include baseline HbA1c value as a covariate, and study drug treatment and stratification factors at randomization (other than the categorized HbA1c) as fixed factors. The mean difference between treatment arms (Gla-300 vs IDeg-100) will be estimated based on the least-squares (LS) means in the ANCOVA model. The estimated differences and their SDs obtained across the imputed datasets will be combined to produce a single point estimate and CI using Rubin's rule and presented with a 2-sided 95% CI and a *P* value.

The tests for non-inferiority will be performed at a 1-sided 2.5% significance level, and the non-inferiority will be demonstrated if the upper bound of the 2-sided 95% CI of the difference between Gla-300 and IDeg-100 treatment arms is $<0.3\%$. Superiority will be established if the upper bound of the 2-sided 95% CI is $<0\%$.

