4.3 PRIMARY ENDPOINT ANALYSIS

4.3.1 Definition of endpoint

The primary endpoint is the change from baseline to Week 24 in HbA1c level. For efficacy assessments of the trial, HbA1c will be measured with blood samples collected at the central laboratory at the time points specified in [Section 5.7](#) (baseline, Week 12, Week 24). If a participant needs to receive a rescue antidiabetic therapy, the HbA1c assessment should be performed before the antidiabetic therapy is introduced. In addition, in case of study drug treatment discontinuation, participants will be followed up per protocol. In case of trial discontinuation, HbA1c assessment will be performed at the time of withdrawal. If HbA1c measurements fall out of windowed assessments (baseline, Week 12, Week 24), the results for those assessments will be excluded (considered as missing for analysis).

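### Protocol 11.2.2 takes patients with a significant deviation out of the trial, not only off study drug, so exits before Day 128 leave no observed Week 24 HbA1c for the treatment-policy estimand

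*Protocol*

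**What the plan says.** Protocol 11.2.2 defines a significant deviation as "nonadherence to the protocol by the patient or investigator that results in a significant, additional risk to the patient". It adds that breaches of the eligibility criteria, local regulations or ICH GCP can be among them. The stated consequence is "and will lead to the patient being withdrawn from the trial", with a cross-reference to Section 4.4.

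The protocol treats stopping study drug and leaving the trial differently:

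- **Stopping study drug (4.4.1.1):** "Patients will be followed up according to the trial procedures specified in this protocol up to the scheduled date of trial completion", or until any adverse event resolves or stabilizes if that is later.
- **Leaving the trial (4.4.3 and 6.1.1):** one early discontinuation visit as soon as possible. On the endpoint itself, "In case of trial discontinuation, HbA1c assessment will be performed at the time of withdrawal, if possible".

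The primary estimand (8.1.2) is the Week 24 difference in HbA1c change "regardless of discontinuation of study drug treatment due to any reasons and use of rescue therapies", estimated in the ITT set.

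SAP 5.4.5.1 (Table 10) assigns Days 72 to 127 to Week 12, and Day 128 onward to Week 24. SAP 4.3.1 treats any HbA1c outside the baseline, Week 12 and Week 24 windows as missing. For patients who stopped treatment, a missing Week 24 value is "imputed using data from patients also discontinuing the study drug treatment but who have their endpoint assessed within each treatment arm" (Protocol 8.7.3.1, repeated in SAP 4.3.2).

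**The concern.** A treatment-policy estimand needs the endpoint from every randomized patient, including those who should not have been enrolled and those affected by a site error. Section 11.2.2 ends collection of that endpoint for exactly such patients, while the ITT definition keeps them in the analysis. Protecting the patient may require stopping insulin. It does not require cancelling HbA1c samples at visits already in the schedule. The missing data are therefore created by the protocol's own wording and could be avoided.

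The imputation is affected in a second way. Followed under 4.4.1.1, these patients would be treatment discontinuers with an observed Week 24 value, which is the group the imputation draws on. Withdrawn before Day 128, they need imputation instead of supporting it. If too few such discontinuers remain in either arm, SAP 4.3.2 allows treatment arm to be dropped from the model and values to be drawn from a normal distribution centred on the patient's baseline, which implies no average change. The trial is open-label at the sites, so a difference between arms in withdrawals cannot be excluded, although nothing in the documents shows one.

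**Working it through.** **1. What happens to the exit HbA1c.** Day 1 is the first dose, and the Week 24 target is Day 169 (SAP Table 10).

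| Exit HbA1c taken on | Counts as | Week 24 value |
|---|---|---|
| Before Day 72 | nothing (outside the HbA1c windows) | imputed |
| Days 72 to 127 | Week 12 | imputed |
| Day 128 or later | Week 24 | observed |

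**2. The plan's own sample size (Protocol 8.3).** Inputs: margin 0.3, SD 1.1, true difference 0, 1-sided alpha 2.5%, power 90%, dropout 10%.

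- Power = Φ(0.3 / (1.1 × √(2/n)) − 1.96). With n = 283: 0.3 / 0.0925 = 3.244, and Φ(1.284) = 90.0%.
- 283 / 0.90 = 314.4, rounded up to 315 per arm, or 630 in total. The plan's figures reproduce.

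**3. Illustrative loss of power.** The documents give no rate of significant deviations, so x = 2, 5 or 10 percentage points, added to the planned 10%, is an assumption.

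*(a) All exits before Day 128.* Observed n per arm = 315 × (0.90 − x), rounded down.

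*(b) Exits spread evenly over 169 days.* Days 1 to 71: 71/169 = 42%. Days 72 to 127: 56/169 = 33%. Days 128 to 169: 42/169 = 25%. The share before Day 128 is 127/169 = 0.75. Week 24 values lost per arm = 315 × x × 127/169, taken from 315 × 0.90 = 283.5 and rounded down.

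| x | (a) n per arm | (a) power | (b) lost per arm | (b) n per arm | (b) power |
|---|---|---|---|---|---|
| 2 points | 277 | 89.4% | 4.7 | 278 | 89.5% |
| 5 points | 267 | 88.3% | 11.8 | 271 | 88.8% |
| 10 points | 252 | 86.5% | 23.7 | 259 | 87.4% |

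**4. Effect on the penalized imputation.** SAP 4.3.3 adds 0.3 to each imputed Gla-300 value. An added share x of missing Gla-300 values therefore moves the estimate against Gla-300 by 0.3 × x, which is 0.006, 0.015 or 0.030 HbA1c points. With even exits (0.3 × x × 127/169) it is 0.005, 0.011 or 0.023.

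**The case against.** The strongest counter-argument is that 11.2.2 is a trial-management paragraph that points to Section 4.4, where the detailed rules are largely discretionary. Section 4.4.3 says patients may withdraw from the trial or from study drug, and may be withdrawn at the investigator's discretion. It does not list significant deviations. The analysis plan also seems to expect some of these patients to finish: the per-protocol set is limited to completers without significant deviations affecting the primary endpoint, and SAP 4.2 reviews such deviations case by case. This shows that the documents are not fully consistent. It does not remove the rule. The list in 4.4.3 is expressly non-exhaustive, its permissive wording does not override a mandatory sentence elsewhere, and the SAP uses a wider definition of significant deviation, for analysis purposes.

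Other points limit the size of the problem, and they stand:

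- The trigger is narrow, since it requires significant added risk, and eligibility waivers are prohibited. The 2, 5 and 10 point scenarios have no basis in the documents.
- A withdrawal a few days before Day 128 could have its exit visit inside the Week 24 window. This is an edge case, because HbA1c is to be taken at withdrawal.
- The imputation also uses the patient's own baseline HbA1c, any Week 12 value, SU use and eGFR stratum.
- The penalized and reference-based analyses partly probe the missing data.
- The sponsor stopped the trial on 27 June 2023 (SAP 1.1), and efficacy is only summarized descriptively (SAP 5.2), so no formal non-inferiority result depends on this.

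**Conclusion.** The concern holds as stated. Read literally, 11.2.2 requires withdrawal from the trial, and an exit HbA1c taken before Day 128 cannot serve as the Week 24 value that the primary estimand needs. These patients stay in the ITT set, so the harm is avoidable reliance on imputation, not exclusion.

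The effect is small: about half a point of power for 2 extra points of withdrawals, and about 2.6 to 3.5 points for 10. These figures are pessimistic. They rest on assumed rates added to the 10% dropout, which may already include some of these patients, and they give no credit for information recovered by imputation. It is a defect of the plan as written, worth correcting because the remedy costs almost nothing.

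**What to change.** Reword 11.2.2 so that a significant deviation leads to stopping study drug where patient safety requires it. State that follow-up then continues under 4.4.1.1, with HbA1c still collected at Week 12 and Week 24, unless the patient withdraws consent or consent was not valid. Exclusion from the per-protocol set already deals with deviations that affect the primary endpoint.

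The cost is one or two sentences and no new visits, since both HbA1c visits are already scheduled. The small downside is that sites keep following patients after a serious deviation. Because the trial has ended, the change can now serve only as a correction for a future protocol that uses the same text.
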